10.3.4 Safety variables

10.3.4.1 Determination of MTD

The objective of the dose selection phase is to determine the maximum tolerated dose (MTD) or confirm that the start dose level of rogaratinib (800 mg b.i.d.) is safe. The MTD is defined as the highest dose that can be given so that toxicity probability is below the target toxicity

23 MAY 2023 Version 6.0 Page: 138 of 181

P_T=30%. Estimation of the MTD will be based on the estimation of the observed dose dependent incidence rate of DLT in the first 21 days of dosing.

The modified toxicity probability interval (mTPI) design (40) will be applied to guide the dose selection decisions in the study. The equivalence interval of the toxicity probability for the MTD is set to [25%, 35%], in which any dose with a toxicity probability falling into this interval is considered as an estimate close to the true MTD. The dose selection part will be finished after 20 patients are evaluable for the MTD assessment. A beta-binomial Bayesian model with Beta(1,1) prior will be used to compute the posterior probabilities that the true rate of DLT is contained in each of the 3 toxicity intervals:

- [0, 25%] under-dosing (below the MTD)
- [25%, 35%] target dosing (close to the MTD)
- [35%, 100%] over-dosing (above the MTD)

The mTPI method calculates the unit probability mass (UPM) for above intervals with safety rules to stop due to excessive toxicity. In addition doses that are estimated to have excessive toxicity will be excluded from the trial.

The UPM for a given interval is defined as the probability of the interval divided by the length of the interval. Then an appropriate dose-finding action will be chosen based on the interval with the largest UPM. Specifically, if the UPM for the under-dosing interval is the largest, the dose is considered lower than the MTD and the recommendation is to escalate to the next higher dose or to stay on the dose level if current dose is the highest possible dose (800 mg b.i.d. being the highest possible dose) (letter E in Table 10–1); if the target dosing interval has the largest UPM, the mTPI design will recommend remaining at the current dose (letter S in Table 10–1); if the over-dosing interval has the largest UPM, the design will recommend de-escalating to the previous lower dose (letter **D** in Table 10–1). If the safety stopping rule is met, the toxicity of the current dose will be considered as unacceptable high and never be used again in the remainder of the trial (letters **DU** in Table 10–1). The safety rule is triggered if the posterior probability that the current dose is above the MTD is greater than 95%. All of these rules are summarized and precalculated in Table 10-1 below. No decision is made before data of at least 4 patients are available on the first dose level and are evaluable for DLTs. The sponsor in consultation with the investigators will decide how many additional patients need to be evaluable for DLTs on the same dose level before the next decision. See Table 7–2 for rogaratinib dose levels.

The decision on the number of additional patients and on the next dose level will be based on the recommendations from the mTPI, clinical assessment, all available PK and safety data.

The dose selection part will be finished after 20 patients are evaluable for DLT assessment and are available for the MTD determination. The RP2D will be defined once sufficient data is available. The final decision about the RP2D will be made by the sponsor in consultation with the investigators.

23 MAY 2023 Page: 139 of 181 Version 6.0

Table 10-1: Possible dose finding actions

	Number of patients treated at current dose																
Number of patients with observed DLTs	4	5	6	7	8	9	10	11	12	13	14	15	16	17	18	19	20
0	Е	Е	Е	Е	Е	Е	Е	Е	Е	Е	Е	Е	Е	Е	Е	Е	Е
1	S	S	Ε	Е	Ε	Ε	Ε	Ε	Е	Ε	Ε	Е	Ε	Ε	Ε	Е	Е
2	S	S	S	S	S	S	S	Ε	Е	Ε	Ε	Е	Ε	Ε	Е	Ε	Е
3	DU	D	S	S	S	S	S	S	S	S	S	S	Ε	Ε	Е	Е	Е
4	DU	DU	DU	D	D	S	S	S	S	S	S	S	S	S	S	S	S
5		DU	DU	DU	DU	DU	D	S	S	S	S	S	S	S	S	S	S
6			DU	DU	DU	DU	DU	DU	D	S	S	S	S	S	S	S	S
7				DU	D	S	S	S	S	S	S						
8					DU	D	S	S	S								
9						DU	S										
10							DU										
11								DU									
12									DU								
13										DU							
14											DU						
15												DU	DU	DU	DU	DU	DU
16													DU	DU	DU	DU	DU
17														DU	DU	DU	DU
18															DU	DU	DU
19																DU	DU
20																	DU

The column represents the number of patients treated at a given dose level in the trial. Each row represents the number of patients treated at the dose level and who have experienced dose-limiting toxicity (DLT) events. The letters in each cell provides the dose-assignment decision based on the data readout from the row and column numbers.

E: Escalate to the next higher dose (or stay if current dose is the highest possible dose)

S: Stay at the same dose

D: De-escalate to the previous lower dose (or stop if current dose is lowest possible dose)

DU: De-escalate to the previous lower dose and the current dose will never be used again.

23 MAY 2023 Version 6.0 Page: 140 of 181

10.3.4.2 Adverse events (AEs)

Individual listings of adverse events will be provided. Adverse events will be reported using MedDRA terms (v.20.0 or later) and graded according to NCI CTCAE v.4.03. The incidence of treatment-emergent adverse events (TEAEs) and treatment-emergent drug-related adverse events (TEADRs), respectively, will be summarized in frequency tables using worst CTCAE v.4.03 grade. Frequency tables will also be provided for the changes of worst CTCAE v.4.03 grade after start of treatment versus baseline.

AEs will be considered to be treatment-emergent if they have started or worsened after first administration of study drug up to 30 days after the last dose of rogaratinib or 90 days after the last atezolizumab administration, whichever comes later.

10.3.4.3 Clinical laboratory evaluations

Laboratory data outside the reference range will be listed with abnormal values flagged. The incidence of laboratory data outside the reference range (low, high) will be summarized in frequency tables. The incidence of laboratory toxicities will be summarized by worst CTCAE v.4.03 grade. Frequency tables will be provided for the changes of worst CTCAE v.4.03 grade after start of treatment versus baseline.

10.3.4.4 Other safety measures

Quantitative data (vital signs, ECG) will be described by the following summary statistics: arithmetic mean, standard deviation, median, minimum and maximum. These summary statistics will be presented for the original data as well as for the difference to baseline. Frequency tables will be provided for qualitative data.

10.3.5 Pharmacokinetic variables

The concentration-times courses of rogaratinib in Cycle 1 will be tabulated by dose level. The following statistics will be calculated for each of the sampling points: arithmetic mean, standard deviation and coefficient of variation (CV), geometric mean, geometric standard deviation (re-transformed standard deviation of the logarithms) and CV, minimum, median, maximum value and the number of measurements. Means at any time will only be calculated if at least 2/3 of the individual data were measured and were above the lower limit of quantification (LLOQ). For the calculation of the mean value a data point below LLOQ will be substituted by one half of this limit. In tables showing mean values, where values below LLOQ are included in the calculation of mean values, these means will be marked.

Individual and geometric mean concentration vs. time curves of all analytes (using the actual sampling times for individual plots and the planned sampling times for mean plots) will be plotted using both linear and semilogarithmic scale.

Pharmacokinetic characteristics (t_{max} , t_{last} , R_{start} , R_{end} , points terminal and %AUC [t_{last} - ∞] excluded) will be summarized by the statistics mentioned above. T_{max} and t_{last} will be described utilizing minimum, maximum and median as well as frequency counts.

Concentration data from Cycle 2 to 5 as well as atezolizumab data will only be listed.

23 MAY 2023 Version 6.0 Page: 141 of 181

10.3.6 Biomarker variables

Biomarker data will be summarized using descriptive statistics and will be graphically displayed if appropriate. The correlation between biomarkers and selected safety, efficacy, or PK parameters may be graphically displayed. Further statistical analyses may be conducted.

10.3.7 Patient-reported outcomes (PRO)

PRO data as measured by the EORTC QLQ-C30 will be analyzed to assess differences in health-related Quality of Life (HRQoL) and health utility values using all available data. The scoring of the PRO endpoints and handling of missing data will be detailed in the statistical analysis plan.

PRO data will be summarized using descriptive statistics and will be graphically displayed if appropriate. Further statistical analyses may be conducted.

10.4 Determination of sample size

This Part A of the study is primarily a descriptive safety and tolerability Phase 1b trial.

No formal sample size calculation has been done for the dose selection part due to the exploratory nature of this Part A of the study. It is expected that up to 20 evaluable patients will be enrolled for safety and for the dose selection part. After 20 patients included in the dose selection, enrollment will continue up to a total of 26-30 patients at the most promising dose with regard to safety and efficacy to obtain additional data on safety, PK, and clinical activity.

A sample size of at least 26 evaluable patients at the MTD/RP2D will lead to a Bayesian posterior probability $P(\pi \le 0.4 \mid data)$ of at least 91% with a power of at least 96% and a Bayesian posterior probability $P(\pi > 0.4 \mid data)$ of at least 92% and with 80% power assuming a true population proportion for the response rate of π_u =0.6 under the alternative hypothesis for the upper criteria and a population proportion of π_l =0.15 under the alternative hypothesis for the lower criteria.

In case that the highest dose of rogaratinib (800 mg b.i.d.) is well tolerated in combination with atezolizumab, it is expected that the minimum of 26-30 evaluable patients is included. Assuming a dropout rate of 15%, a total minimum sample size of approximately 30 patients at the MTD/RP2D is expected.

Based on tolerability, different rogaratinib starting doses may be explored in this study. And in addition to FGFR testing, tumor tissue will be tested for further potential predictors of response (e.g. PIK3CA mutations). If, for example, the most promising rogaratinib dose or patient subgroups are not clearly defined, approximately 20 additional patients may be enrolled up to a total of 50 patients to confirm signals in a larger sample size, when rogaratinib in combination with atezolizumab seems to be tolerated and early signs of clinical activity have been observed. This decision will be made by the Sponsor after consultation with the investigators.

All calculations were performed with SAS 9.4 using non-informative Jeffrey's priors.

23 MAY 2023 Version 6.0 Page: 142 of 181

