9.2.2.5 End-of-treatment (EOT) visit		
9.6.3 Further safety		
9. Procedures and variables	After primary completion, C ≥5	The primary completion safety
Table 9.2 Schedule of evaluations: Treatment and follow-up periods	and EOT 12-lead ECG are considered optional and at the investigator's discretion	data (as per cut date of July 2021) did not identify myocarditis or any other cardiac event as a safety
9.2.2.3 Cycles ≥ 5		signal.
9.2.2.5 End-of-treatment (EOT) visit		Optional ECG will give the flexibility for the investigators to use this resource as needed
9.6.3 Further safety		in addition to the management guidance provided on table 7-10.
9. Procedures and variables Table 9.2 Schedule of evaluations: Treatment and follow-up periods Footnote f 9.2.2.3 Cycles ≥ 5 9.2.2.5 End-of-treatment (EOT) visit	After primary completion, the frequency of ophthalmologic examinations was reduced: The examination is performed on D1 of every 4 th instead of every 2 nd cycle, starting at C2. At the EOT visit, ophthalmologic examination is done only in case the patient reports changes in vision.	After primary completion, the patients that are currently in the study have been on treatment for at least 2 years, therefore, the chance of developing new ophthalmologic issues is small. In case of reported changes in vision, ophthalmological examinations will be performed.

23 MAY 2023 Version 6.0 Page: 168 of 181

Section # and Name	Description of Change	Brief Rationale
 9. Procedures and variables Table 9.2 Schedule of evaluations: Treatment and follow-up periods Footnote h 9.2.2.3 Cycles ≥ 5 	After primary completion, hormone panel (thyroid function test) done periodically to reduce frequency of testing, according to local standard of care.	After primary completion, the testing frequency can be reduced and will be done according to local standard of care. The detection of asymptomatic thyroid function abnormality will rely on AE assessment at each visit. The investigators can order ad hoc TSH, T3 and T4 when hypothyroidism or hyperthyroidism is suspected based on symptomatic AE collection and decide the action to be taken for atezolizumab.

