5.1 Assignment of analysis sets

Final decisions regarding the assignment of subjects to analysis sets will be made during the review of study data and documented in the final list of important deviations, validity findings and assignment to analysis set(s) (see section **4.6**).

All subjects who signed the informed consent form (ICF) for FGFR testing will be included in the 'All enrolled subjects' evaluations. All subjects assigned to treatment will be included in the 'All subjects assigned to treatment' evaluations.

Safety analysis set (SAF)

All subjects who received at least one dose of study drug (i.e. rogaratinib or atezolizumab) and have post-treatment safety data available will be included in the safety evaluation.

MTD analysis set (MTD)

All subjects who completed Cycle 1 and who took at least 80% of the required total dose (protocol-defined dose reductions will not be considered incompliant) of either study drug (rogaratinib or atezolizumab) during Cycle 1 or discontinued during Cycle 1 due to a DLT will be included in the MTD evaluation.

Only subjects from the dose selection part are to be considered for the MTD analysis set.

Efficacy analysis set (EFS)

All subjects who have received at least one dose of study drug and who have post-baseline efficacy data available will be included in the efficacy evaluation.

Pharmacokinetics analysis set (PKS)

All subjects who have received at least one dose of study drug and with at least one valid concentration after first dosing and no important protocol deviations affecting the validity will be included in the PK evaluation.

6. Statistical Methodology

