6.2 Efficacy

Efficacy analyses will be performed on the EFS, unless otherwise specified.

All efficacy variables evaluated using the Response Evaluation Criteria in Solid Tumors (RECIST) version 1.1 are linked to the secondary and exploratory objectives of the study Part A. All variables evaluated using the Response Evaluation Criteria in Solid Tumors Modified for Immune-based Therapeutics (iRECIST) version 1.1 are exploratory only.

Efficacy data will be summarized using descriptive statistics and will be graphically displayed if appropriate. The correlation between pharmacodynamic parameters and selected safety, efficacy, or PK parameters may be graphically displayed. Further statistical analyses may be conducted.

Response as defined by RECIST version 1.1: complete response (CR), partial response (PR), stable disease (SD), progressive disease (PD). Response and progression will be evaluated in this trial using the new international criteria proposed by the RECIST committee for solid tumor.

iRECIST defines new response categories, including iUPD (unconfirmed progressive disease) and iCPD (confirmed progressive disease). For purposes of iRECIST assessment, the first visit showing progression according to RECIST 1.1 will be assigned a visit (overall) response of iUPD, regardless of which factors caused the progression.

Best overall tumor response according to RECIST criteria will be summarized using frequency counts. Best % change in Target Lesion sum of diameter from baseline will be displayed graphically for all subjects from worst to best in a waterfall plot.

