6.2.2 Secondary Efficacy Variable

The efficacy variable linked to the secondary objective of this study is the objective response rate.

Objective response rate (ORR) is defined as the percentage of subjects whose best response is either a CR or PR. Subjects for whom best tumor response is not CR or PR, as well as subjects without any efficacy assessment will be considered non-responders. According to RECIST version 1.1, confirmation of PR and CR is not required considering the nature of the study and the protocol requirements.

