Kaplan-Meier (KM) product-limit estimates for median, 25th and 75th percentile with its 95% CI together with total number of subjects, total censored and total events will be provided for PFS per dose group. In addition KM survival curves will be presented for each dose group.

Overall survival (OS) is defined as the time (days) from start of study treatment to death due to any cause. Subjects alive at the date of data cut-off for analysis will be censored at the last date known to be alive. If a subject is lost to follow-up before any assessment after assignment to treatment, this subject will be censored at day 1.

KM product-limit estimates for median, 25th and 75th percentile with its 95% CI together with total number of subjects, total censored and total events will be provided for OS per dose group. In addition KM survival curves will be presented for each dose group.

Time to progression (TTP) is defined as the time (days) from start of study treatment to date of first observed disease progression (radiological or clinical). TTP for subjects without disease progression at the time of analysis will be censored at the last date of tumor evaluation. TTP for subjects who have no tumor assessments after baseline will be censored at day 1.

KM product-limit estimates for median, 25th and 75th percentile with its 95% CI together with total number of subjects, total censored and total events will be provided for TTP. In addition KM survival curves will be presented for each dose group.

Time to Response (TTR) is defined as the time (days) from start of study treatment to the date of first observed partial or complete response. Only subjects with a partial or complete response are considered for TTR.

KM product-limit estimates for median, 25th and 75th percentile with its 95% CI together with total number of subjects, total censored and total events will be provided for TTR. In addition KM survival curves will be presented for each dose group.

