6.4.5 Other Safety Data

Quantitative data (such as vital signs, electrocardiogram) will be described by the following summary statistics: arithmetic mean, standard deviation, median, minimum and maximum. These summary statistics will be presented for the original data as well as for the difference to baseline. Frequency tables will be provided for qualitative data, such as ECG findings and interpretation.

The average of triplicate quantitative ECG parameters at all ECG time points will be used for all analyses.

ECOG performance status will be summarized by visit for observed values and changes from baseline using summary statistics. Ophthalmologic interpretation will be tabulated in frequency tables.

Number of women taking a pregnancy test and the result will be tabulated by visit.

7. Document history and changes in the planned statistical analysis

- SAP, Version 1.0, 19 JUN 2018

- SAP Amendment, 02 APR 2020
 - Wording was harmonized throughout the document;
 - Added wording changes from protocol amendment 2;
 - Added definitions for pre-screening failures and screening failures;
 - Added information on the validity review meeting;
 - Clarified that only subjects from the dose selection part are to be considered for the MTD analysis set;
 - Planned analysis for prior immunotherapy, duration of treatment, TTP, dose modifications;
 - Added plan for the biomarker/pharmacodynamics analysis.
- SAP Amendment, 05 OCT 2021
 - PK concentration data of only rogaratinib (previously also atezolizumab) will be tabulated in Cycle 1
 - Addition of TTR definition
 - Addition of Covid-19 analyses
 - Wording change: patient replaced by subject
 - Specification of CSP reference: Section 7.4.3
- SAP Supplement, 05 APR 2022
 - Section 2: Addition of wording about part B not being conducted
 - Section 6.1.1: Addition of presentation of countries and study centers
 - Section 6.1.2: Deletion of NYHA in demographic variables
 - Section 6.1.2: Deletion of status of primary tumor and clinical status at study entry in cancer baseline characteristics
 - Section 6.1.3: Addition of wording about therapies during follow-up
 - Section 6.2.3: Addition of Follow-up time definition and more detailed wording
 - Section 6.2.4: Addition of visits of the summary statistics of EORTC QLQ-C30 and the analysis set
 - Section 6.4.2: Deletion of frequency tables for change of CTCAE grade from pre-treatment

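### SAP 6.2.2 does not settle the ORR denominator against the efficacy analysis set; as a smaller wording point, the power figures in Protocol 10.4 are right at 26 evaluable patients but not at every larger size in the planned 26-30

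*Protocol*

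**What the plan says.** **ORR denominator**

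- SAP 6.2: "Efficacy analyses will be performed on the EFS, unless otherwise specified".
- SAP 5.1 defines the EFS as subjects with at least one dose of study drug "who have post-baseline efficacy data available will be included in the efficacy evaluation". Protocol 10.2 has the same definition.
- SAP 6.2.2, on ORR: "subjects without any efficacy assessment will be considered non-responders". Protocol 10.3.3.1 has the same rule. Neither names an analysis set.
- SAP 6.2.3, on OS: "If a subject is lost to follow-up before any assessment after assignment to treatment, this subject will be censored at day 1". The same section censors time to progression at day 1 for subjects with no tumor assessment after baseline.
- Protocol 6.4.2 and SAP 4.2 allow replacement of subjects without an efficacy assessment.

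**Power statement**

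- Protocol 10.4: "A sample size of at least 26 evaluable patients at the MTD/RP2D will lead to a Bayesian posterior probability" that the response rate is at most 0.4 of at least 91%, with power of at least 96% at a true rate of 0.15. It also gives a posterior probability that the rate exceeds 0.4 of at least 92%, with 80% power at a true rate of 0.6. The prior is Jeffreys.
- The same section adds that, if the highest dose is well tolerated, "it is expected that the minimum of 26-30 evaluable patients is included", and it assumes 15% dropout.

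**The concern.** ORR is the only secondary efficacy variable, and two careful analysts could compute it on different denominators. One would follow SAP 6.2 and use the EFS. The other would follow SAP 6.2.2 and keep treated subjects who were never assessed, counting them as failures. The first approach silently removes early dropouts, who cannot be responders, so any difference runs in one direction: upwards.

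The sample-size sentence attaches its figures to a minimum of 26, and the section then plans 26 to 30. With a discrete outcome, more patients do not always mean more power at a fixed posterior level. It was therefore worth checking whether the printed figures hold across that range.

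**Working it through.** **1. The denominator passages side by side**

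A subject with a dose but no efficacy assessment is a non-responder under SAP 6.2.2 and Protocol 10.3.3.1. The same subject generally fails the EFS definition in SAP 5.1 and Protocol 10.2, and so is not in the population that SAP 6.2 names. On the EFS as defined, the non-responder rule has essentially no one to apply to. The day-1 censoring rules in SAP 6.2.3 and the replacement rule show that such subjects are expected.

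With r responders among m assessed subjects and k treated but unassessed, the EFS gives r/m and the non-responder rule gives r/(m+k). Since r/m ≥ r/(m+k), the EFS figure is never lower.

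Illustration. The documents give no value for k. Protocol 10.4 plans about 30 patients with 15% dropout, and 30 × 0.85 = 25.5, so I take m = 26 and let k run from 0 to 4. With r = 14:

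| Unassessed k | Denominator | ORR |
|---|---|---|
| 0 (EFS) | 26 | 14/26 = 53.8% |
| 1 | 27 | 14/27 = 51.9% |
| 2 | 28 | 14/28 = 50.0% |
| 3 | 29 | 14/29 = 48.3% |
| 4 | 30 | 14/30 = 46.7% |

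Under the Jeffreys prior, the posterior probability that ORR exceeds 0.4 falls from 0.924 (14 of 26) to 0.773 (14 of 30).

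**2. The figures in Protocol 10.4**

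Inputs, all from 10.4: reference rate 0.4; true rates 0.6 (upper) and 0.15 (lower); posterior levels 92% and 91%; Jeffreys prior Beta(0.5, 0.5).

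After x responses in n patients the posterior is Beta(x + 0.5, n − x + 0.5).

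- Upper: take the smallest x with P(rate > 0.4) ≥ 0.92. Power is the binomial probability of x or more at 0.6.
- Lower: take the largest x with P(rate ≤ 0.4) ≥ 0.91. Power is the binomial probability of x or fewer at 0.15.

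At n = 26 the plan's figures reproduce. Fourteen or more responders give a posterior of 0.9239 and power of 0.8007. Seven or fewer give 0.9158 and 0.9679.

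Across the planned range at the same posterior levels:

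| n | Upper cut-off | Upper posterior | Upper power | Lower cut-off | Lower posterior | Lower power |
|---|---|---|---|---|---|---|
| 26 | ≥14 | 0.924 | 80.1% | ≤7 | 0.916 | 96.8% |
| 27 | ≥15 | 0.949 | 75.0% | ≤7 | 0.935 | 96.0% |
| 28 | ≥15 | 0.927 | 81.3% | ≤7 | 0.951 | 95.1% |
| 29 | ≥16 | 0.951 | 76.6% | ≤8 | 0.916 | 97.8% |
| 30 | ≥16 | 0.931 | 82.5% | ≤8 | 0.935 | 97.2% |

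Reverse check, moving each cut-off by one to recover the power:

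- n = 27, ≥14 responders: power 85.5%, but posterior 89.5%.
- n = 29, ≥15 responders: power 86.4%, but posterior 90.0%.
- n = 28, ≤8 responders: lower power 98.2%, but posterior 89.3%.

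So no cut-off delivers the printed upper pair at 27 or 29, or the printed lower pair at 28.

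Sensitivity to the upper posterior level: at 91% the sizes below 80% power are again 27 and 29; at 90% only 27; at 89% none.

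**The case against.** **On the denominator.** SAP 6.2 allows exceptions, and the specific rule in 6.2.2 may be one. The time-to-progression rule supports this, because it too provides for subjects with no post-baseline assessment. Early death or clinical progression might also count as efficacy data, which would bring some unscanned subjects into the EFS. SAP 5.1 leaves final set assignment to a documented data review. These readings are reasonable, and the first is probably what was meant. What stands is that the SAP states neither. Even the second leaves out a subject lost with no information at all.

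**On the power.** Quoting operating characteristics at the minimum size is normal practice. The printed 92% and 91% look like the values attained at 14 and 7 of 26, cut to whole percents, and 10.4 never calls them decision thresholds. For the upper criterion it says 80% power, not at least 80%. The calculation is anchored at 26, since 26/0.85 = 30.6 is close to the 30 planned. All of this stands and limits the point to wording. Read literally, though, the sentence claims more than holds at 27, 28 and 29.

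**Stronger readings to avoid.** A reader might infer that the sample-size calculation is wrong or the study too small. It is not wrong: every figure reproduces at 26, and the dips are a binomial saw-tooth. A reader might infer that the reported ORR is inflated. The documents show only that it could be, since they give no count of unassessed subjects. A reader might also infer that naming an all-treated denominator now is post hoc, because the safety data cut was July 2021 and the SAP history ends with "SAP Supplement, 05 APR 2022". The non-responder rule is already in Protocol 10.3.3.1, and SAP section 7 lists no change to 6.2.2 in that supplement, so the rule needs no such label.

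**Conclusion.** The denominator gap is real and is the main point. The direction is certain: ORR on the EFS is equal to or higher than ORR under the stated non-responder rule. The size is not known. With 26 assessed and 14 responders it runs from nothing to 7.2 percentage points (53.8% − 46.7%, before rounding) as the unassessed go from 0 to 4, and those counts are assumptions.

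The power point is a wording matter. The figures in 10.4 are correct at 26. At the same posterior levels, upper power over 26-30 runs from about 75% to 82% and lower power from about 95% to 98%. The upper shortfalls at 27 and 29 depend on keeping the level at 91% or 92%.

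Severity is minor for both. Part A is descriptive, plans no confirmatory analysis and has no ORR decision rule, so no go/no-go decision changes.

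**What to change.** **SAP 6.2.2.** Add: *ORR will be calculated with all treated subjects as denominator, subjects without any efficacy assessment counting as non-responders, as in Protocol 10.3.3.1; ORR in the EFS will be shown alongside.*

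This costs one sentence and one extra table line, with no new data. The headline ORR will be equal or lower. The power in 10.4 concerns evaluable patients, so it does not describe the all-treated figure.

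**Protocol 10.4.** Tie the quoted posterior and power figures to 26 evaluable patients by dropping the words that make 26 a minimum. If a range is wanted, note that at the same posterior levels upper power is about 75-82% and lower power about 95-98% over 26-30. Word this as description only, so that 92% and 91% do not become decision thresholds that the sponsor never set. This is a text edit with no effect on enrolment; its only cost is a less favourable figure at 27 and 29 for the upper criterion and at 28 for the lower.
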